**Supportive analysis no. 1: Stratified difference of response rates 95% CI**

In order to further characterize the dose-response, the proportion of ACR20 response at Week 12 will also be presented for each treatment group, along with the stratified difference in ACR20 response proportion between each evobrutinib dose and placebo, and the 2-sided 95% CI for the difference [Evobrutinib – Placebo].

The following will be presented: stratified Δ between response rates for pairwise comparisons versus placebo, the 2-sided 95% CI, and nominal p-value. As there are 3 regions (Western Europe, US, ROW), the number of strata is equal to K=3.

For each pairwise comparison, the difference of response rate will be computed using the formula no. (7), available in Lu 2008. By denoting A the 1st treatment group (evobrutinib 25 mg QD, evobrutinib 75 mg QD or evobrutinib 75 mg BID) and B the treatment group of comparison (placebo), the difference in response rate is the weighted average of differences within strata. It can be written as

$$\hat{\delta} = \frac{\sum_{j=1}^K W_j (r_{Aj} - r_{Bj})}{\sum_{j=1}^K W_j}$$

, where  $r_{Aj}$  represents the response rate of the treatment group A in the strata j, and  $W_j$  represent the CMH weight of the stratum j. This CMH weight must be calculated using the formula no. (9), available in Lu 2008, and then standardized to have a sum equal to 1:

$$W_j^{CMH} = \frac{\left[ \frac{1}{n_{Aj}} + \frac{1}{n_{Bj}} \right]^{-1}}{\sum_{j=1}^K \left[ \frac{1}{n_{Aj}} + \frac{1}{n_{Bj}} \right]^{-1}}$$

, where  $n_{Aj}$  represents the sample size of the strata j for the treatment group A ( $n_{Bj}$  for treatment B respectively).

Once  $\hat{\delta}$  is calculated, the chi-square statistic is given by the formula no. (1), available in Lu 2008. Consider the following hypotheses  $H(\delta): \pi_{Aj} - \pi_{Bj} = \delta$  for  $j = 1, \dots, K$ , we obtain

$$X^2(\delta) = \frac{[\sum_{j=1}^K W_j (r_{Aj} - r_{Bj} - \delta)]^2}{\sum_{j=1}^K W_j^2 \tilde{V}_{r_{Aj} - r_{Bj}}}$$

where

$$\tilde{V}_{r_{Aj} - r_{Bj}} = \left\{ \frac{\tilde{R}_{Aj}(1 - \tilde{R}_{Aj})}{n_{Aj}} + \frac{\tilde{R}_{Bj}(1 - \tilde{R}_{Bj})}{n_{Bj}} \right\} \frac{N_j}{(N_j - 1)}$$

denotes the variance of  $r_{Aj} - r_{Bj}$  under the hypothesis  $H(\delta)$ ,  $\tilde{R}_{Aj}$  and  $\tilde{R}_{Bj}$  are the constrained maximum likelihood estimates of  $\pi_{Aj}$  and  $\pi_{Bj}$  so that  $\tilde{R}_{Aj} - \tilde{R}_{Bj} = \delta$ ,  $W_j$  is the CMH weight for stratum  $j$ , and  $N_j$  is the total number of subjects in stratum  $j$ . The MN weights will not be used to compute the chi-square statistic, in order to avoid an additional iterative process.

For each stratum  $j$ , the constrained maximum likelihood estimates are computed as follows, as described in [Farrington 1990](#):

$$\tilde{R}_{Aj} = 2u \cos(w) - b/3a$$

$$\tilde{R}_{Bj} = \tilde{R}_{Aj} - \delta$$

, where

$$w = (\pi + \cos^{-1}(\vartheta/u^3))/3$$

$$\vartheta = (b^3/3a)^3 - bc/6a^2 + d/2a$$

$$u = \text{sign}(\vartheta) \sqrt{b^2/(3a)^2 - c/3a}$$

$$a = 1 + \theta$$

$$b = -(1 + \theta + r_{Aj} + \theta r_{Bj} + \delta(\theta + 2))$$

$$c = \delta^2 + \delta(2r_{Aj} + \theta + 1) + r_{Aj} + \theta r_{Bj}$$

$$d = -r_{Aj} \delta(1 + \delta)$$

$$\theta = n_{Bj}/n_{Aj}$$

Finally, the confidence limits based on MN method can be obtained by solving the equation (3), available in [Lu 2008](#). Indeed, considering  $\alpha = 0.05$ , if we denote  $\chi_{1,0.95}^2$  the 95th percentile of the

chi-square distribution with one degree of freedom, then we reject  $H(\delta)$  if  $X^2(\delta) > \chi_{1,0.95}^2$ . The 2-sided 95% confidence limits of  $\delta$  can be obtained by solving

$$X^2(\hat{\delta}_L) = X^2(\hat{\delta}_U) = \chi_{1,1-\alpha}^2$$

To solve this equation, an iterative process must be implemented to reach the lower and upper bounds of the 95% CI, ie the  $\delta$  must vary between  $(-1 ; 1)$ , bounds excluded, until the equation is verified. This will provide the values of the lower bound  $\hat{\delta}_L$  and the upper bound  $\hat{\delta}_U$ .

A sample code to calculate this 2-sided 95% CI is available in Appendix 18.5. It is based on the example provided in Garner 2016.

For each pair-wise comparison, the statistical hypothesis test can be written as follows:

$\left\{ \begin{array}{l} H_0: \text{there is no significant difference of response rate between treatment A and B, ie, } \delta = 0 \\ H_1: \text{there is significant difference of response rate between treatment A and B, ie, } \delta \neq 0 \end{array} \right.$

If we denote  $x$  the result the equation (1) in Lu 2008, then the p-value is given by  $P(X > x)$  where  $X$  follows a chi-square distribution with one degree of freedom.

### **Supportive analysis no. 2: Tipping Point**

Subjects with reason of treatment discontinuation related to safety or efficacy will be considered as non-responders.

Tipping point analysis will be performed as in Yan 2009, Section 2.3.2.

Let

$n_1 =$  number of responders out of missing data due to various reasons for placebo

$n_2 =$  number of responders out of missing data due to various reasons for evobrutinib 25 mg QD

$n_3 =$  number of responders out of missing data due to various reasons for evobrutinib 75 mg QD

$n_4 =$  number of responders out of missing data due to various reasons for evobrutinib 50 mg BID

The same analysis method as the primary analysis of the ACR20 at Week 12 will be performed using the mITT Analysis Set for each possible combination of  $n_1$ ,  $n_2$ ,  $n_3$  and  $n_4$ .

Using the Hochberg procedure, the values of  $n_1$ ,  $n_2$ ,  $n_3$  and  $n_4$  where the study result will be tipped from statistically significant (not statistically significant) to not statistically significant (statistically significant) will be assessed for plausibility based on the corresponding response rate from each treatment.

---

**Supportive analysis no. 3: Stratified difference of response rates with imputed ACR components using multiple imputations (MAR pattern)**

The same method for estimating stratified difference of response rates will be applied, but the ACR components will be imputed using multiple imputations process (MI SAS procedure) with MAR pattern, as if they follow their original assignment of treatment group.

Data will be imputed for subjects with reason of discontinuation unrelated to safety or efficacy. Subjects with reason of treatment discontinuation related to safety or efficacy will be considered as non-responders.

The SAS code is available in Appendix 18.5.

The multiple imputations will be performed as follows:

1. Monotone missing data structure will be created as follows: intermediate (non-monotone) missing data will be multiply imputed using the Markov chain Monte Carlo (MCMC) method and assuming MAR and multivariate normality. Transformation of data will only be used if there is a clear deviation from normality. The SAS procedure PROC MI with the MCMC option will be used with seed number=PPD. The number of burn-in iterations will be set to 200, which is the default value. Nevertheless, if diagnosis plots show that the convergence has not yet occurred, this will be adjusted. The ACR components must be pre-specified in the following order, the last one being the most significant component:
  - i. Physical function (as assessed using the HAQ-DI) from Week 2 to Week 12
  - ii. Patient's Global Assessment of RA Disease Activity from Week 2 to Week 12
  - iii. Physician's Global Assessment of RA Disease Activity from Week 2 to Week 12
  - iv. Pain (as assessed using the Patient's Assessment of Arthritis Pain VAS) from Week 2 to Week 12
  - v. hsCRP from Baseline to Week 12
  - vi. Tender Joint Count (of 68 joints assessed) from Baseline to Week 12
  - vii. Swollen Joint Count (of 66 joints assessed) from Baseline to Week 12
2. Then, each component will be imputed with treatment group and data at previous visit from all ACR20 components as covariates.
3. Imputation will be repeated N=1000 times. The ACR20 will then be calculated for each of the data sets from the imputed components.
4. Single proportion and associated 95% CI of each treatment arm will be computed using EXACT BINOMIAL from FREQ procedure with SAS. The 95% CI will be used to compute the standard error of each proportion for the N=1000 imputations.
5. The difference of response rate compared to placebo and associated 95% CI based on stratified MN method will be computed for each of the N=1000 imputations. The 95% CI

will be used to compute the standard error of the difference of response rate compared to placebo.

- Results will be combined using MIANALYZE SAS procedure with the Rubin's rules.

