- For the summary of ACR20 responders (Yes) at Week 12, the number and percentage of subjects from each treatment group who have met the responder criterion (at least 20% improvement from baseline) for each ACR component will be provided.
- For the summary of ACR20 non-responders (No) at Week 12, the number and percentage of subjects from each treatment group who are imputed as non-responders due to different reasons (i.e., discontinued due to adverse event, lack of efficacy, etc) will be provided.

A bar chart will be generated by treatment group to present the cumulative proportion of subjects achieving ACRx where x is the cut-off of percentage reduction from baseline for ACR as a composite endpoint. The bar chart will start with x=20%, incremented by 10%, and up to the maximum observed percentage of improvement. Vertical lines will be drawn at 20%, 50% and 70%.

The number of responders/non-responders (Yes, No) at Week 2, Week 4 and Week 8 will also be presented in the logistic regression table using the LOCF-NR method.

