#### **Supportive analysis no. 4: Stratified difference of response rates with imputed ACR components using multiple imputations (MNAR pattern)**

The same method as in Supportive analysis no. 3 will be considered, but this time with MNAR pattern. Subjects' missing data due to early discontinuation will be imputed, using data available from the placebo arm, regardless of reason for study discontinuation.

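### The variable order printed for the ACR20 multiple imputation (SAP 14.1, supportive analyses 3 and 4) runs by component and contradicts the visit-by-visit model in step 2

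*SAP*

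**What the plan says.** Supportive analysis no. 3 (SAP 14.1) imputes the ACR components and then derives ACR20. Its stated aim is that subjects be imputed "as if they follow their original assignment of treatment group".

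- **Step 1** creates a monotone structure: "intermediate (non-monotone) missing data will be multiply imputed using the Markov chain Monte Carlo (MCMC) method and assuming MAR and multivariate normality". It adds: "The ACR components must be pre-specified in the following order, the last one being the most significant component". The first entry is "Physical function (as assessed using the HAQ-DI) from Week 2 to Week 12". Patient global, physician global, pain, hsCRP and tender joints follow, and the last entry is "Swollen Joint Count (of 66 joints assessed) from Baseline to Week 12". hsCRP and the two joint counts are listed from Baseline, the other four components from Week 2. Step 1 names no treatment term.
- **Step 2** brings in treatment: "each component will be imputed with treatment group and data at previous visit from all ACR20 components as covariates".

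Supportive analysis no. 4 keeps this method, but dropout data are imputed "using data available from the placebo arm, regardless of reason for study discontinuation". The sample code in Appendix 18.5 is redacted in the public copy.

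**The concern.** Whether a pattern counts as monotone depends on the order of the variables: once one is missing, every later one must be missing too. Dropout is monotone if variables are listed visit by visit. It is not monotone if they are listed component by component, because a subject who leaves early still has early-visit values of components that come later in the list.

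The list as printed would therefore send most dropout data to the step 1 MCMC, which is meant only for intermittent gaps. In no. 3, six components would be imputed with no treatment term stated. In no. 4, the same six would already be filled under MAR before the placebo-based step began. Neither analysis would then test what it is described as testing. These are the two multiple-imputation checks on a primary analysis that uses LOCF with non-responder imputation.

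**Working it through.** **Inputs.** The list order is from step 1. For the early visits, the SAP's primary analysis text says: "The number of responders/non-responders (Yes, No) at Week 2, Week 4 and Week 8 will also be presented". With Week 12 that gives four post-baseline visits, which agrees with SAP Table 47. The plan states no figure for this point, so there is none to reproduce.

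**Size of the list.** Four components × 4 visits + three components × 5 visits = 16 + 15 = 31 variables.

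**Counting rule.** A missing value that precedes the subject's last observed variable in the list is non-monotone and goes to step 1. Later ones go to step 2. In the printed order, the last observed variable of any dropout is a swollen joint count, because that block comes last and includes Baseline. All missing values of the other six components precede it.

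| Last visit | Missing (7 × visits left) | Step 1, printed order (6 × visits left) | Step 2, printed order | Step 1, visit order |
|---|---|---|---|---|
| Baseline | 28 | 24 | 4 | 0 |
| Week 2 | 21 | 18 | 3 | 0 |
| Week 4 | 14 | 12 | 2 | 0 |
| Week 8 | 7 | 6 | 1 | 0 |

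The share is 6/7 = 86% at every dropout time, and this needs no assumption about the data.

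**Compatibility with step 2.** Each of the 7 × 4 = 28 post-baseline variables needs the previous visit's values of all components. In the printed order, any variable other than a swollen joint count needs at least the previous swollen joint count, which stands later in the list. So 24 of 28 lack covariates that come before them, and only the four swollen joint variables have them. At Week 2 the list also has no baseline value for four of the seven components.

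**Illustration of size.** A large-sample simulation used 40,000 subjects per arm, ACR20 of 30% on placebo and 60% on evobrutinib, and 11% dropout (rates from SAP 8.2.1). Dropout was random and spread evenly over last visits at Baseline and Weeks 2, 4 and 8. Correlations between components were assumed, and every dropout was imputed. The true difference was 0.3052.

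| Analysis | Order; step 1 | Arm difference | Dropout response, placebo / evobrutinib |
|---|---|---|---|
| No. 3 | visit | 0.3031 | 0.311 / 0.599 |
| No. 3 | printed; no treatment | 0.2873 | 0.417 / 0.562 |
| No. 4 | visit | 0.2822 | 0.297 / 0.397 |
| No. 4 | printed; no treatment | 0.2865 | 0.421 / 0.558 |
| No. 3 | printed; by arm | 0.3055 | 0.294 / 0.604 |
| No. 4 | printed; by arm | 0.3037 | 0.299 / 0.592 |

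- No. 3, no treatment in step 1: 0.3031 − 0.2873 = 0.0158, or 1.6 points. The parts agree: 0.11 × (0.417 − 0.311) + 0.11 × (0.599 − 0.562) = 0.0117 + 0.0041.
- No. 4, no treatment in step 1: 0.2865 − 0.2822 = 0.0043, or 0.4 points. The net shift is small because both arms' dropouts move up: 0.11 × (0.558 − 0.397) = 0.0177 against 0.11 × (0.421 − 0.297) = 0.0136.
- No. 4, step 1 by arm but printed order kept: 0.3037 − 0.2822 = 0.0215, or 2.2 points. Adding treatment to step 1 repairs no. 3 but not no. 4; the order must change as well.

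A second simulation, with 10% stopping and other assumed correlations, moved the arm difference by less than 1 point. For no. 4 it gave 42–45% response in evobrutinib dropouts against 41% in visit order, where the table above gives 56% against 40%. The two agree on direction but not on size.

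**The case against.** The strongest reply is that the list ranks components and does not dictate a 31-variable sequence. The visit ranges may only say which visits of each component enter the model. SAP section 3 supports this: version 2.0 added baseline hsCRP and joint counts as covariates, and those are exactly the three components listed from Baseline. A ranking applied within each visit would make step 1, step 2 and no. 4 coherent. The redacted code would settle both the order and the handling of treatment, and redaction is not a gap in the plan. The stated aim of no. 3, to follow the assigned group, may also be meant to govern step 1.

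Most of this stands. It makes a visit order the likely intention, and it means that the absence of treatment from step 1 is inferred from silence. It does not remove the conflict in the text: the order is mandatory, each entry spans visits, and nothing says that the ranking applies within a visit. A programmer who follows the list as printed gets an imputation that step 2 does not describe.

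A reader might go further and infer that the sensitivity analyses were programmed wrongly, or that no. 4 is in effect a MAR analysis. The documents support neither. The implementation cannot be seen. On the second inference the simulations disagree: in one, nos. 3 and 4 nearly coincide under the printed order (0.2873 and 0.2865); in the other, no. 4 stays close to its control-based result.

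**Conclusion.** The SAP text for supportive analyses 3 and 4 contradicts itself. The six-of-seven split is exact if the printed order is followed. That it was followed, and that step 1 ran without treatment, is unconfirmed.

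The numerical effect is probably small: about 0.4 to 1.6 points on the arm difference at 11% dropout with no treatment in step 1, and under 1 point at 10% in the other simulation. These sizes rest on assumed correlations and dropout timing. In no. 3 they probably overstate the effect, because subjects who stop for safety or efficacy reasons are set to non-responder and so fewer are imputed.

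The primary LOCF-NR analysis, its Hochberg decision and the tipping-point analysis do not use this imputation. Nos. 3 and 4 carry nominal p-values only. The point is minor and confined to these two analyses.

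**What to change.** In SAP 14.1 no. 3, step 1, give the variable list visit by visit: baseline values, then all seven components at Week 2, Week 4, Week 8 and Week 12. Say that the listed component order applies only within a visit. Say which baseline values are included, since step 2 asks for all components at the previous visit. State that step 1 is run by treatment group and is limited to intermittent gaps, so that all dropout data pass to step 2 in no. 3 and to the placebo-based model in no. 4. Check that the Appendix 18.5 code matches.

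The cost is SAP wording and, if the code uses the printed order, a reordered variable list. No extra data are needed.

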#### **Supportive analysis no. 4: Stratified difference of response rates with imputed ACR components using multiple imputations (MNAR pattern)**

The same method as in Supportive analysis no. 3 will be considered, but this time with MNAR pattern. Subjects' missing data due to early discontinuation will be imputed, using data available from the placebo arm, regardless of reason for study discontinuation.

#### **Supportive Analysis no. 5: Non-parametric method – Cochran-Armitage test**

A monotonic dose-response relationship, between ordered treatment groups and proportion of responders will be assessed via the Cochran-Armitage trend test ([Dörner 2017](#)). The p-value reported tests the null hypothesis that the proportion of ACR20 responders is the same across treatment groups, against the alternative that the proportion is ordered (from smallest value to largest) according to increasing treatment group. In the Cochran-Armitage test, missing data are handled the same as in the main logistic modeling analysis.

For this Cochran-Armitage trend test, the proportion of ACR20 response rate, the p-value (asymptotic) will be presented.

An example of SAS code is available in Appendix [18.5](#).

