### Treatment Sequences

Eligible subjects will be randomly assigned in a 1:1:1:1 ratio to 1 of the 4 parallel treatment groups (N = 90/group), as detailed in [Table 3](#), in combination with their stable background MTX therapy. Subjects and Investigators will be blinded to the initial treatment assignment.

**Table 3** Treatment Groups and Regimens

Treatment Group	Regimen a,b
1	Evobrutinib 25 mg QD
2	Evobrutinib 75 mg QD
3	Evobrutinib 50 mg BID
4	Placebo

MTX = methotrexate.

a All subjects will continue to take their MTX background therapy along with trial treatment per treatment group.

b To maintain the study blind, all subjects will receive BID treatment. For subjects with QD treatment assignments, 1 dose a day will be study drug and 1 will be placebo.

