## Evobrutinib

### Phase IIb in Rheumatoid Arthritis MS200527-0060

---

Eligible subjects will be randomized into 1 of 3 evobrutinib arms (25 mg once daily, 75 mg once daily, or 50 mg twice daily) or the placebo arm in a ratio of 1:1:1:1 stratified by whether or not they are in the MRI substudy (Yes, No) and by region (US, Western Europe, Japan, and the rest of world), so that within each treatment arm, there will be approximately 90 subjects, with approximately 45 subjects included in the MRI substudy to ensure approximately 80 evaluable subjects per arm for the primary analysis, and approximately 40 evaluable subjects per arm for the MRI analysis.

To ensure an adequate number of evaluable MRI subjects in the MRI substudy, recruitment of non-MRI subjects into the study may be capped. If a subject's baseline MRI indicates lack of osteitis and synovitis, additional subjects may be added to the MRI stratum to account for these subjects. Should the MRI substudy recruitment prove more difficult than anticipated, the Sponsor reserves the right to terminate the MRI substudy. Should this be done, all sites would be allowed to recruit non-MRI subjects into the study.

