## **8.5 Description of Statistical Analyses**

### **8.5.1 General Considerations**

A general description of the statistical methods to be used to analyze the efficacy and safety data is outlined below. Prior to locking of the database for the study, a detailed SAP will be finalized.

Any changes to the data analysis methods described in the protocol will require an amendment only if a principal feature of the protocol is affected. Any other changes to the planned data analysis that does not require a protocol amendment will be described in the SAP and the CTR. Additional exploratory analyses will be conducted as deemed appropriate.

A 2-sided  $\alpha$  level of 0.05 will be applied for tests of treatment effect within the study.

For the purpose of statistical analyses, baseline is defined as the last assessment prior to first dose.

In general, continuous variables will be summarized descriptively using the number of observations (N), mean, standard deviation (SD), median, first quartile (Q1), third quartile (Q3), minimum, and maximum. Categorical variables will be summarized using frequency counts and percentages.

Statistical analysis will be performed using the computer program package SAS® System for Windows (version 9.4 or higher; SAS Institute, Cary North Carolina, USA).

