### **8.2 Definition of Analysis Sets and Subgroups**

#### **8.2.1 Sample Size**

The primary endpoint of the trial is the ACR20 response at Week 12. A sample size of 80 evaluable subjects per group will provide approximately 90% power at an  $\alpha$  of 0.05, 2-sided significance level to detect a difference in Week 12 ACR20 response proportion between evobrutinib- and placebo-treated subjects, assuming a placebo response proportion of 30% to 45% and an expected treatment benefit of 30%, after adjusting for multiple comparisons of 3 dose comparisons with placebo. For the same range of placebo response rate, the sample size of 80 evaluable subjects per group will also provide adequate power (approximately 80%) for the expected difference of 25%. To account for reduced information provided by the Modified Intent-to-Treat (mITT) analysis set, due to subject dropout and protocol noncompliance, occurring at a rate of approximately 11% over a 12-week period, approximately 90 subjects per group will be enrolled.

[figure not shown]

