### **Primary analysis: logistic regression**

For the primary analysis, the estimate of the odds ratio (OR), together with the associated 2-sided 95% CI, nominal p-value and adjusted p-value, comparing each evobrutinib dose group to placebo, will be provided based on a logistic regression model for the odds of ACR20 response, with treatment group as a factor and adjustment based on region. An example of SAS code is available in Appendix 18.5.

Missing data will be handled using LOCF-NR as follows: each component will be imputed using post-baseline LOCF (ie, baseline value cannot be used for missing data imputation). Then the ACR20 will be re-calculated using imputed components. Subjects who prematurely discontinued from treatment will be considered as non-responders.

A family-wise Type I error rate (FWER) at the primary analysis will be controlled at the 2-sided 0.05 significance level for the 3 pairwise comparisons of evobrutinib dose versus placebo, using the Hochberg procedure (see Hochberg 1990).

The statistical test comparing each evobrutinib group to placebo can be written as follows:

$$\begin{cases} H_0: OR = 1.0 \\ H_1: OR \neq 1.0 \end{cases}$$

Consider the ordered two-sided p-values (from lowest to highest) that arise from comparing the 3 comparisons on the basis of the primary endpoint:  $p_{(1)} \leq p_{(2)} \leq p_{(3)}$ . The Hochberg's step-up method proceeds as follows:

1. Step 1: If  $p_{(3)} < 0.05$  reject  $H_{(1)}$ ,  $H_{(2)}$  and  $H_{(3)}$  (i.e., conclude all evobrutinib dose groups are more effective than placebo under the condition the OR are  $> 1$ ) and then stop; otherwise go to Step 2.
2. Step 2: If  $p_{(2)} < 0.025$  reject  $H_{(1)}$  and  $H_{(2)}$  (i.e., conclude doses associated with  $H_{(1)}$  and  $H_{(2)}$  are more effective than placebo under the condition the OR are  $> 1$ ) and then stop; otherwise go to Step 3.
3. Step 3: If  $p_{(1)} < 0.0167$  reject  $H_{(1)}$  (i.e., conclude that only one of the dose groups associated with  $H_{(1)}$  is more effective than placebo under the condition the OR is  $> 1$ ) and stop

Hochberg procedure will be computed with SAS® (see Appendix 18.5). Adjusted p-values will not be presented for any analyses based on PP analysis set.

In addition, the number and percentage of ACR20 responders (Yes/No) at Week 12 will be summarized by treatment group.

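### The supportive dose-trend test is specified without region, although randomisation and the primary model both account for it; stratifying it by region is a small, free improvement

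*SAP*

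**What the plan says.** Protocol section 8.2 randomises subjects "stratified by whether or not they are in the MRI substudy (Yes, No) and by region". It lists four regions. The SAP works with three (US, Western Europe, rest of world) because the sponsor decided not to recruit in Japan (SAP section 7).

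The primary analysis in SAP section 14.1 is a logistic regression with treatment and region. Type I error is controlled "for the 3 pairwise comparisons of evobrutinib dose versus placebo, using the Hochberg procedure". SAP section 7 removes MRI substudy participation as a covariate from all efficacy analyses and gives the reason. Supportive analysis no. 1 accordingly stratifies the differences in response rate by region alone, with three strata.

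Supportive analysis no. 5 says that a monotone dose response "will be assessed via the Cochran-Armitage trend test", with an asymptotic p-value. It names no stratum. Its row in SAP Table 13 pairs a stratified Miettinen-Nurminen interval for each difference from placebo with the two-sided Cochran-Armitage p-value. The sample code for this test in Appendix 18.5 is blacked out, so only the text can be read.

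**The concern.** Dose response is part of the primary objective, and this test is one of two that address its overall shape. The other is MCP-MOD (supportive analysis no. 6), whose description also names no region covariate.

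The Cochran-Armitage variance is built from the pooled response rate. That variance includes differences between regions, which stratified randomisation has already balanced across arms. If regions differ in ACR20 response, the test statistic is divided by too large a standard error. The protocol's reason for stratifying is that these factors may affect outcomes, so the sponsor itself allows for this. At stake is some efficiency in a supportive p-value and its consistency with the region-adjusted analyses around it.

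**Working it through.** **Inputs from the documents.** Two-sided alpha: "level of 0.05 will be applied for tests of treatment effect within the study" (Protocol 8.5.1). Allocation: "Eligible subjects will be randomly assigned in a 1:1:1:1 ratio to" four arms (Protocol 5.1). Size: "A sample size of 80 evaluable subjects per group will provide approximately 90% power at an" two-sided alpha of 0.05, "assuming a placebo response proportion of 30% to 45% and an expected treatment benefit of 30" points (SAP 8.2.1). The same size "will also provide adequate power (approximately 80%) for the expected difference of 25" points.

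**The plan's own figure.** No power is stated for the trend test, so the pairwise figure is checked. With n = 80 and alpha = 0.05/3 = 0.0167 (z = 2.394), the pooled chi-squared formula is

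power = Φ{[|p2 − p1| − z√(2·p̄(1 − p̄)/n)] / √([p1(1 − p1) + p2(1 − p2)]/n)}.

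For 30% against 60%: (0.300 − 2.394 × 0.0787)/0.0750 = 1.49, which gives 93.2%. Over placebo rates of 30% to 45%, a 30-point benefit gives 92.9% to 94.0%, or 90.4% to 91.7% with continuity correction. A 25-point benefit gives 78.7% to 79.7% by the pooled formula. Dropout: 80/(1 − 0.11) = 89.9, so 90 per arm. The stated figures are reproduced, given that they are described as approximate.

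**Why the unstratified test is conservative.** Let w_j be the share of region j and p_j its response rate. The pooled variance splits as

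p̄(1 − p̄) = Σ w_j p_j(1 − p_j) + Σ w_j (p_j − p̄)².

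With arms balanced within region, only the first term is real sampling variance. The unstratified z then has standard deviation √[Σ w_j p_j(1 − p_j) / p̄(1 − p̄)], which is at most 1.

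Two examples use assumed shares of 10/20/70% and an overall rate of about 45%:

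- Odds ratio 2 per region step, rates 21/35/51%: p̄ = 0.448; within-region variance 0.0166 + 0.0455 + 0.1749 = 0.2370; pooled variance 0.2473; ratio 0.958, square root 0.979. Null rejection rate: 2Φ(−1.96/0.979) = 0.045. Simulation gives 0.046.
- Odds ratio 5 per step, rates 5/21/57%: p̄ = 0.446; within-region variance 0.0048 + 0.0332 + 0.1716 = 0.2095; pooled variance 0.2471; ratio 0.848, square root 0.921. Null rejection rate: 2Φ(−1.96/0.921) = 0.033. Simulation gives 0.034.

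**Power by simulation.** 40,000 trials per scenario, 80 per arm, three regions balanced across arms, a treatment odds ratio common to all regions, two-sided 0.05. This table uses shares of 10/20/70%, placebo 45% and scores 0/25/75/100. Each cell gives unstratified then region-stratified rejection, in percent.

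| Effect at top dose | Region OR 1 | OR 2 | OR 3 | OR 5 |
|---|---|---|---|---|
| +30, graded | 99.3 / 99.3 | 99.4 / 99.4 | 99.5 / 99.7 | 99.7 / 99.9 |
| +30 at all doses | 95.5 / 95.4 | 95.7 / 96.1 | 96.3 / 97.1 | 97.0 / 98.3 |
| +25, graded | 95.1 / 95.1 | 95.4 / 95.9 | 96.0 / 97.0 | 96.8 / 98.1 |
| +20, graded | 81.8 / 81.8 | 82.1 / 83.2 | 83.1 / 85.7 | 84.2 / 88.5 |
| None | 5.2 / 5.2 | 4.6 / 5.0 | 4.0 / 5.0 | 3.4 / 5.0 |

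Varying the region shares (equal or 10/20/70%), the placebo rate (30% or 45%), the scores (0/1/2/3 or 0/25/75/100) and the graded shape widens the gain from stratification:

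- about 0 to 2.6 points at a graded +25 to +30;
- 0 to 2.2 points at +30 in all doses;
- about 0 to 9 points at a graded +20, of which about 1 to 2 points at odds ratio 2.

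The upper ends belong to odds ratio 5. Under the null, the unstratified test rejects at about 0.05 with no region effect, 0.041 to 0.048 at odds ratio 2, and about 0.02 to 0.04 at odds ratio 5. The stratified test stays near 0.05.

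**The case against.** The test is only supportive. It lies outside the Hochberg family and no decision rule depends on it. The confirmatory comparisons already adjust for region, and dose response is also described by region-stratified differences and by MCP-MOD. All of this stands, and it limits the importance of the point.

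At the planned effects the unstratified test already has high power, and the documents offer no evidence on how much regions differ. That also stands. Odds ratio 5 per step implies placebo rates from 5% to 57% in the example above, which is an extreme assumption. The 20-point case is still relevant, since the SAP uses 20% as the improvement that defines the minimum effective dose.

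The interval and the trend p-value in Table 13 address different hypotheses: pairwise differences against an ordered trend over four arms. They would not correspond one to one even with identical strata. This is correct, so the shared row shows uneven handling of region and not a contradiction.

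The blacked-out code might contain a stratified version. That cannot be excluded, but the SAP text specifies the test and describes no strata.

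A reader might infer that both randomisation factors belong in the test. The documents do not support that. MRI participation was removed from the efficacy analyses with a stated reason, and a six-stratum trend test would match neither the primary model nor the three-stratum interval beside it.

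**Conclusion.** The point holds as a free improvement. As described, the trend test ignores region, while the randomisation, the primary model and the neighbouring interval all use it. If region is prognostic, the p-value is conservative and some power is lost: about 0 to 2.6 points at the planned 25 to 30 points with a graded response, and about 0 to 9 points at a graded 20. If region is not prognostic, the two versions are practically the same. These sizes rest on assumed region shares, region odds ratios of 1 to 5 per step, a common treatment odds ratio and assumed dose-response shapes.

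A reader might infer that the trial gives away material power for its primary objective. The documents do not support this: the test is supportive, its power at the planned effects is already about 92% or more in the scenarios examined, and the error is in the safe direction. Nor is any false-positive risk created.

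**What to change.** In SAP Table 13 and supportive analysis no. 5, replace the Cochran-Armitage test by a 1-df trend test stratified by region only: the CMH correlation statistic with three strata, as in supportive analysis no. 1. State the treatment scores. Do not add MRI substudy as a stratum. If the sponsor prefers to keep the present test, the SAP should say that the p-value is unstratified and why.

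The cost is one PROC FREQ statement and a sentence in the SAP. No extra data or subjects are needed, and there is essentially no loss of power when region does not matter.
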